Aim 1: To develop the transition of care model for Hispanic/Latino adults, patients and providers will be selected from Duke Regional Hospital (DRH) and Duke University Health System (DUHS), the local Hispanic/Latino community, and local clinics in Durham delivering care to Hispanic/Latino patients with diabetes. Drs. [name] and [name] will collect the data. It is anticipated that a total of 15 participants (4 patients) and (6 providers - physicians [MD, DO], nurse practitioners (NPs), and physician assistants (PAs)) will be obtained. We seek to explore patients' and providers' perspectives on the transition of care from hospital to community. All participants will complete a brief questionnaire. The information collected will be instrumental in developing a transition of care model that is culturally/patient centered.

Aim 2: Overall common themes have been collected from the 4 patient participants and 6 provider participants interviews and questionnaires thus far. Providers and patients uniformly expressed a need for a simple discharge summary that is more visual and in Spanish, language barriers and financial constraints.

Duke CTSI will conduct a Community Consultation Studio with community Engaged Research Initiative Core as a part of Pro00103450. They will interview 6-8 participants from Hispanic/Latino communities with diabetes. The common themes from this interview along with the common themes from the first 10 participants in this protocol will be combined to develop a transition of care model.

The first set of 16 participants will be discharged on the newly developed model based on interviews and data collected already and CTSI CCS protocol Pro00103450. The participants will be asked to complete a set of questionnaires and a 30-day post discharge telephone interview.

This interactive approach will use the Plan-Do-Study-Act (PDSA) framework. Changes can be reassessed and modified swiftly as a part of the continuous improvement cycle to allow for adjustments that facilitate the desired outcomes.

The second set of 16 participants will be discharged on a model based on the first 16 participants experience and feedback. Five participants enrolled in the first set will be re-interviewed to assess their feedback regarding the process. Based on this information the TOC model will be revised.

The second set of participants will complete a set of questionnaires and a 30-day post discharge phone interview similar to the first set of participants.

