General Data Analytics. The recording will be reviewed by the Co-PI, each independently, they will identify themes and will color code them. Subsequently themes will be combined into common themes.

Analysis. For all outcomes and demographic information collected, descriptive analysis (means and standard deviations for continuous variables and frequencies and percentages for categorical variables) overall and by randomization arms. The non-feasibility outcomes will be compared

between the usual care and intervention group. Chi-squared or Fisher's Exact tests will be conducted to assess the differences of each outcome between groups. Logistic regression models will be conducted to access the adjusted differences of each outcome between usual care and intervention groups. The models will be adjusted for a limited number of variables that are theoretically thought to explain some variation in the value of the outcomes.

For Aim 2 we would like to ensure that we are able to at minimum detect a difference in the primary outcomes in the number of Emergency Department visits and hospital re-admissions.

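### Aim 2 discharges all 32 patients on a version of the new model and defines no usual-care group, so the planned comparisons with usual care cannot be estimated from the enrolled data

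*Combined protocol and SAP*

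**What the plan says.** **Design.** Under Design & Procedures, Aim 2, "The first set of 16 participants will be discharged on the newly developed model". The next 16 are discharged on a version revised in the light of the first set's feedback, within a Plan-Do-Study-Act cycle. Subject Recruitment and Compensation sets Aim 2 enrolment at 32. No allocation procedure is described. Apart from the analysis text, the only mention of randomization is in Risk/Benefit Assessment, and it concerns larger trials in the future.

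**Hypotheses.** Purpose of the Study states four Aim 2 outcomes on which the new model should do better than usual discharge: emergency visits, unplanned 30-day readmission, follow-up visits with a provider, and patient experience.

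**Analysis.** Data Analysis & Statistical Considerations plans:

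- descriptive summaries "overall and by randomization arms";
- a two-group comparison: "The non-feasibility outcomes will be compared" "between the usual care and intervention group";
- chi-squared or Fisher tests: "Exact tests will be conducted to assess the differences of each outcome between groups";
- adjusted models: "Logistic regression models will be conducted to access the adjusted differences of each outcome between usual care and intervention groups";
- covariate adjustment: "The models will be adjusted for a limited number of variables";
- a closing goal to "at minimum detect a difference in the primary outcomes in the number of Emergency Department visits and hospital re-admissions".

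**The concern.** The analysis text is written for a two-arm randomized study, whereas the design text describes one intervention given in two successive versions. The statistical methods are named, but one of the two groups they would compare does not exist among the enrolled patients and is not defined anywhere else.

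This reaches the primary outcomes. The goal of detecting a difference in emergency visits and readmissions has no contrast behind it. An analyst who follows the plan must either run a two-group test on one group or find a comparator that the plan does not describe. In the second case its source, period, size and eligibility could be settled after the intervention outcomes are known. In the first, a p-value of 1 that carries no information could be read as showing no difference.

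**Working it through.** **Inputs.** First set 16 and second set 16 (Design & Procedures, Aim 2); total 32 (Subject Recruitment and Compensation, Aim 2). No event rate is needed for steps 1 to 5.

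**1. Head count.** 16 + 16 = 32, which reproduces the stated enrolment exactly. Usual-care patients among those enrolled: 32 − 16 − 16 = 0.

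**2. Fisher's exact test.** Suppose k of the 32 patients have an event. The table is [k, 32 − k] for intervention and [0, 0] for usual care. Given the margins, the probability of this table is C(32, k) × C(0, 0) / C(32, k) = 1. It is the only possible table, so p = 1 for each of the 33 values k = 0 to 32. The odds ratio is undefined.

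**3. Chi-squared.** Expected count = row total × column total / N. For usual care this is 0 × k / 32 = 0 and 0 × (32 − k) / 32 = 0. The statistic divides by these counts, so it is undefined in all 33 tables.

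**4. Logistic model.** With logit(p) = β0 + β1·G and G = 1 for all 32 patients, only the sum β0 + β1 can be estimated. The design matrix has rank 1 of 2. Adding 1, 2 or 3 covariates gives rank 2 of 3, 3 of 4 and 4 of 5. Adjustment does not recover the group effect.

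**5. Reach in the text.** Six sentences make up the analysis plan, counting the closing goal. Three name the missing grouping outright: the randomization arms, the usual-care comparison and the logistic models. The other three (the tests, the covariates and the detection goal) depend on it by context. In the first sentence only the overall summary survives.

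**6. What if a comparator were added?** This is an illustration only. The documents give no rates, alpha or power, so the rates below and a two-sided alpha of 0.05 are assumptions.

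| Event rate, usual care vs new model | Exact Fisher power, 32 vs 32 | Per group for 80% power (normal approximation, no continuity correction) |
|---|---|---|
| 20% vs 10% | 10.9% | 199 |
| 30% vs 15% | 21.5% | 121 |
| 40% vs 20% | 32.9% | 82 |
| 50% vs 25% | 46.0% | 58 |
| 50% vs 10% | 93.5% | 20 |

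With an equal-sized comparator, a halving of risk gives less than 50% power at each of these rates. Among the cases tried, only the fall from 50% to 10% gives high power.

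**The case against.** The best reply is that much of this is omission and not contradiction. The hypotheses and the analysis both name usual discharge as the comparator. The figure of 32 counts people recruited and enrolled, and patients drawn from records would not be enrolled. On that reading only the reference to randomization arms truly conflicts with the design, and the rest is an undescribed external group. The calculations then merely restate that one group is empty.

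Part of this stands. A records cohort is not ruled out, and the type of comparator is stated in advance, so what could be chosen post hoc is the actual group. The calculations do follow from the zero count; their use is to show that no planned test or adjustment gets round it.

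The reply does not rescue the plan. The documents give no external group a source, period, size, eligibility or method of outcome capture. Slicer Dicer appears only as a way of finding participants. The Aim 1 patients were interviewed to help build the model and are not described as controls. A comparison of set 1 with set 2 sets one version of the intervention against another, in sequence and without randomization. A records cohort would not be a randomization arm either.

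It is also fair to say that this is a minimal-risk pilot and that overall description remains possible. That limits the harm but does not make the stated primary comparison executable. Finally, the documents do not show whether the design text or the analysis text is the error, so the choice of remedy belongs to the sponsor.

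**Conclusion.** The concern holds: the plan contradicts itself and must be corrected before outcomes are analysed. Usual-care patients among those enrolled: 0 of 32. Randomized patients: 0 of 32. Aim 2 comparative outcomes without a defined comparator: 4 of 4. On the enrolled data none of the planned tests or models yields a contrast with usual care, for any pattern of events.

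This rests on reading the two sets of 16 as the whole Aim 2 sample, which the stated total confirms, and on there being no comparator elsewhere in the documents. It does not depend on any assumed event rate; the power figures bear only on the second remedy. It is no criticism of the two-cycle design, which is reasonable groundwork for a later randomized trial.

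**What to change.** **Recommended: align the analysis with the design.** The enrolment and Aim 2 procedures can stay as they are.

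In Data Analysis & Statistical Considerations:

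1. Replace the grouping by randomization arm with grouping by model version (set 1, set 2).
2. Delete the four sentences on the usual-care comparison, the chi-squared/Fisher tests, the logistic models and the covariate adjustment.
3. Replace the closing goal with an estimation goal, for example: *Aim 2 will estimate 30-day emergency visits and readmissions; it is not designed to detect a difference from usual care.*
4. Report 30-day outcomes by version and overall, using patients with 30-day data as the denominator. Give exact 95% confidence intervals for any emergency visit and any readmission, and descriptive summaries for the number of emergency visits.
5. Label any contrast of set 1 with set 2 as exploratory and confounded with calendar time.

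In Purpose of the Study, recast the general hypothesis and the four Aim 2 comparisons as questions for the later randomized trial.

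*Cost:* a text amendment, with no change to enrolment or procedures. The study gives up its comparative hypotheses and its detection goal, and its claim becomes descriptive.

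**Alternative, if a comparison is to be kept.** Before outcomes are analysed, specify by amendment a usual-care records cohort, labelled as non-randomized, with its source, period, size and eligibility. Remove the reference to randomization arms here too. Restrict the comparison to emergency visits and readmissions recorded in the health system's own electronic records for both groups, because the 30-day telephone survey captures outside care only for enrolled patients. Confirm that those records can supply the outcomes. Keep reported follow-up visits and patient experience descriptive. State the selection and calendar-time limits, and either justify the detection goal with stated rates or withdraw it, since 32 intervention patients may be too few.

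*Cost:* an amendment, data extraction and eligibility matching. The result stays open to selection and calendar-time bias.

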A Transition of Care Model from Hospital to Community for Hispanic/Latino Adult Patients with Diabetes

Document Date: November 9, 2021

NCT04864639

Purpose of the Study

The prevalence of diabetes in adults over the age of 20 is significantly higher in the Hispanic/Latino population compared to non-Hispanic whites. Admitted patients with diabetes are at higher risk for readmission and Emergency Department (ED) visits than those without diabetes especially those in lower socioeconomic status and racial/ethnic minority groups. The goals of this proposed study are to explore patients and providers perceptions (n=15, 6 providers and 4 patients) of the current discharge process which will inform the development of a patient-centered transition of care model for Hispanic /Latino adults (≥ 18 years of age) with diabetes from hospital to the community. It is hypothesized that a culturally tailored transition of care model tailored for Hispanic/Latinos adults with diabetes will result in fewer ED visits, hospital admissions, and re-admissions.

The objective remains the same for Aim2. Our hypothesis is that participants enrolled in the newly developed transition of care model will have less Emergency Room visits post discharge, lower rates of unplanned readmission at 30 days post discharge and will report more follow up visits with a health care provider within 30 days of discharge than those individuals discharged on the usual transition of care plan. In addition, patient experience will be better in those in the new transition of care model.

Background & Significance

The prevalence of diabetes in adults over the age of 20 is significantly higher in the Hispanic/Latino population compared to non- Hispanic whites. Diabetes imposes a large economic burden partially due to the significantly higher rates of hospital admission compared to those individuals without diabetes. In 2014, a total of 7.2 million hospital discharges were reported with diabetes as any listed diagnosis among U.S. adults aged 18 years or older. Admitted patients with diabetes are at higher risk for readmission and Emergency Department (ED) visits than those without diabetes especially those in lower socioeconomic status, racial/ethnic minority groups, history of prior admission, diabetes associated comorbidities, public insurance, and emergent or urgent admission.

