identify participants with a recent hospitalization. Patient word of mouth may also be used from local Hispanic organizations. Both methods have been previously implemented by Co-PI ([name]) while enrolling Hispanic/Latino participants in research studies. Approximately 6 health care providers will be recruited from the DRH and Duke University Hospital. We aim to enroll a diverse group of providers including MDs, DOs, NPs and PAs. Providers will be approached for recruitment by the Co-PIs or designated trained research staff. Both inpatient and outpatient providers will be targeted. Compensation will be \$10 per person. If the participant is not interested in sharing their social security number with the research team they will receive a gift of similar monetary value.

Aim 2: Participants will be recruited using Slicer Dicer or the inpatient diabetes admission list. Trained key personnel on the study will introduce the potential subjects to the study. A total of 32 subjects will be recruited and enrolled. The subjects will be compensated \$25 dollars from petty cash for their participation. For the re-interviews (providers) will receive \$10 dollars.

Risk/Benefit Assessment

This is a minimal risk study. We will not include vulnerable populations.

This study should result in better understanding of factors that impact the transition of care of Hispanics/Latinos patients with diabetes. Identifying and understanding internal and external barriers to the transition of care should be determined when considering designing a culturally sensitive transition of care model. A better method to transition from inpatient setting to home for Hispanic/Latinos with regard to factors such as lower socioeconomic status, language, and health literacy along with a fragmented delivery system may result in better outcomes during the transition phase from acute to the outpatient setting.

The benefits to the subject are that the participant may require fewer visits to the ED and less admissions to the hospital in the 30 days following their hospitalization.

The importance of this study is to optimize the transition of care of Hispanic/Latino patients with diabetes because it is poorly understood. This study will inform a more aligned discharge and follow-up process for Hispanic/Latino patients discharge in future and will also inform future larger randomized trials.

Data Analysis & Statistical Considerations

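### Aim 2 sets detecting a difference in ED visits and readmissions as its minimum, but a design of 32 participants lacks that property except for very large effects from high base rates

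*Combined protocol and SAP*

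**What the plan says.** Four parts of the combined protocol and SAP bear on this point.

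- **Detection aim.** The last paragraph of Data Analysis & Statistical Considerations says of Aim 2: "we would like to ensure that we are able to at minimum detect a difference in the primary outcomes". The outcomes named are ED visits and hospital readmissions. This is the only statement in the plan that links sample size to inference.
- **Size and treatment.** Subject Recruitment and Compensation states: "A total of 32 subjects will be recruited and enrolled". Design & Procedures splits them in sequence: "The first set of 16 participants will be discharged on the newly developed model", then "The second set of 16 participants will be discharged on a model based on the first 16 participants experience and feedback". Both sets therefore receive a version of the new model.
- **Hypothesis and analysis.** Purpose of the Study hypothesises superiority over the usual plan: "participants enrolled in the newly developed transition of care model will have less Emergency Room visits post discharge". The Analysis paragraph says "The non-feasibility outcomes will be compared" "between the usual care and intervention group", by chi-squared or Fisher's exact tests and then adjusted logistic regression.
- **Later use.** Risk/Benefit Assessment says the study "will also inform future larger randomized trials".

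The plan gives no base rate, target difference, alpha, power or dropout allowance. It mentions randomisation arms and usual care, but describes no randomisation, usual-care group or historical cohort.

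**The concern.** An aim to ensure a minimum ability to detect a difference is a design requirement, and nothing in the plan shows that 32 participants meet it. Two groups of 16, or one group of 32, look far too small for yes/no 30-day outcomes unless the effect is very large.

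The planned tests compare intervention with usual care, and nothing marks them as exploratory. If they are run at low power, a non-significant result is weak evidence but could be read as showing that the model does not work. A significant result would require a large observed difference and would tend to exaggerate the benefit. Either could distort planning of the larger trial that this study is meant to inform.

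**Working it through.** **Plan's own figure.** The 32 cannot be reproduced, because the documents give none of the inputs to a sample size calculation. What follows is conditional power.

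**Inputs from the documents.** N = 32; two sets of 16; outcomes at 30 days; Fisher's exact test among the named methods.

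**Assumptions.** Usual-care 30-day risk of 20%, 30% or 40%; a halving as a large effect; two-sided alpha 5%; each outcome analysed as yes/no; no dropout; no multiplicity adjustment for two primary outcomes. The last two favour the plan.

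**Step 1: two groups.** Exact Fisher power is the sum over all (x, y) with Fisher p ≤ 0.05 of Bin(x; n, p₁) × Bin(y; n, p₂).

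**Step 2: 32 against a perfectly known rate p₀.** This is the best case for 32 participants. Take the largest c with P(X ≤ c | 32, p₀) ≤ 0.025. Power is then P(X ≤ c | 32, p₀/2).

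- p₀ = 20%: c = 1 (tail 0.0071). Power = 0.9³² + 32 × 0.1 × 0.9³¹ = 0.034 + 0.122 = 0.156.
- p₀ = 30%: c = 4 (tail 0.0189). Power at 15% = 0.464.
- p₀ = 40%: c = 7 (tail 0.0248). Power at 20% = 0.698.

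**Power to detect a halving**

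| Comparison | 20% to 10% | 30% to 15% | 40% to 20% |
|---|---|---|---|
| 16 v 16 (model version 1 v version 2) | 4.7% | 8.7% | 12.6% |
| 32 v hypothetical 32 usual care | 10.9% | 21.5% | 32.9% |
| 32 v perfectly known rate | 15.6% | 46.4% | 69.8% |

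The first row is the only contrast that the enrolled participants provide, and it is not the hypothesis.

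**Step 3: what would be detectable.**

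- 16 v 16: with 0/16 events in one set, the other needs 5/16 (31%) for p < 0.05 (5 v 0: p = 0.043; 4 v 0: p = 0.10). From 20% or 30%, 80% power is not reached even if the true rate falls to zero (20% and 55%).
- 32 v 32: from 20%, power is 64% even at a true rate of zero.
- 32 v a known rate: 80% power needs a fall from 20% to about 2.6% (check: 0.9742³² + 32 × 0.0258 × 0.9742³¹ = 0.433 + 0.367 = 0.80), from 30% to about 9.8%, or from 40% to about 17.8%.

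**Step 4: size needed for two equal groups.** For 80% power, n per group = [1.96√(2p̄(1−p̄)) + 0.8416√(p₁(1−p₁) + p₂(1−p₂))]² / (p₁−p₂)². For 20% to 10%, this is (1.96 × 0.505 + 0.8416 × 0.5)² / 0.01 = 1.990 / 0.01, or 199. For 30% to 15% it is 121, and for 40% to 20% it is 82.

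**Step 5: precision of 32.** Clopper–Pearson 95% intervals: 6/32 = 18.8% (7.2% to 36.4%); 16/32 = 50% (31.9% to 68.1%), the widest, with half-width (68.1 − 31.9)/2 ≈ 18 points.

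**The case against.** The strongest reply is that a reader might infer that 32 participants cannot detect a difference under any comparison, or that a non-significant result is almost certain even if the model halves returns to hospital. The documents support neither.

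- **High base rates.** Against a known rate, a halving from 40% has 70% power. A halving from 50% has 74% (85% at one-sided 5%). Against 1,000 external controls, 80% power is reached for 40% to 17% (normal approximation). Purpose of the Study describes a population at raised risk, so high rates cannot be excluded. These cases still need a very large effect and an external comparator that the plan does not mention.
- **Counts.** The ED outcome is worded as a number of visits. On a Poisson approximation, 32 against a fixed mean has 59% power to detect a halving from 0.5 visits per patient, and 87% from 1.0. The planned chi-squared, Fisher and logistic methods point to a yes/no analysis, but the plan does not settle this.
- **Tone and purpose.** The sentence is an aim, not a claim that a difference will be found. Aim 2 is framed as iterative improvement, descriptive summaries are planned, and a larger trial is foreseen. No passage says that a null result would be reported as no effect, so misreading is a risk and not a prediction.
- **Another remedy.** The authors could keep the aim by defining a usual-care comparator and giving a power calculation. That is legitimate, but it is a different and probably larger study, as Step 4 shows.

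These points limit the claim. They do not supply the missing calculation or comparator.

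**Conclusion.** The closing paragraph is wrong as written: it sets a minimum property for Aim 2 that the design does not have, except for very large effects from high base rates. At assumed risks of 20% to 30%, power to detect a halving stays below 50% in all three comparisons, ranging from 5% (set against set) to 46% (against a perfectly known rate). At 40% it ranges from 13% to 70%.

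The power figures rest on assumed base rates, a two-sided 5% level and a yes/no outcome, none of which the plan states. The absence of a calculation and of a described usual-care group rests on the documents alone. The conclusion is that a non-significant result would be largely uninformative; it is not that detection is impossible.

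**What to change.** Replace the last paragraph of Data Analysis & Statistical Considerations with wording such as:

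> Aim 2 (32 participants) is a pilot and is not sized to detect a difference in ED visits or readmissions. The 30-day proportions will be reported with exact 95% confidence intervals (for example, 6/32 = 18.8%, 7.2% to 36.4%; widest half-width about 18 points). No efficacy conclusion will be drawn from a significance test.

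Two further changes belong in the same edit, or the document will contradict itself:

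1. In the Analysis paragraph, remove the usual-care versus intervention chi-squared, Fisher and logistic analyses, or mark them as exploratory.
2. In Purpose of the Study, mark the superiority hypothesis as one for the later randomised trial.

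Optionally, make feasibility proportions the headline results, each with an exact interval: consented among those approached, discharged with the model delivered, and 30-day interview completed.

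The cost is wording in two sections, with no added participants or procedures. The downside is a less favourable claim, since Aim 2 would carry no efficacy statement.
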